Alternative hypothesis (H_1) : Ratio $(\text{post-booster}/\text{pre-booster}) > 2$

Each of the 2 Booster Groups, CoV2 preS dTM-AS03 (B.1.351) or CoV2 preS dTM-AS03 (D614 + B.1.351), will be tested separately. The superiority will be demonstrated for either or both of the Booster Groups(s) if the lower limit of the two-sided 98.3% CI of the ratio of serum neutralization titer is great than 2.

For each of the Booster Groups, the conditional secondary objective will be reached if both non-inferiority and superiority testing described above are demonstrated. For CoV2 preS dTM-AS03 (D614 + B.1.351), the approach is used across strains (B.1.351 and D614) (if the SARS-CoV-2 D614G variant remains in circulation globally based on reports from authorities [eg, WHO]) or only on the B.1.351 variant.

If the primary immunogenicity objective in participants primed with the Pfizer/BioNTech vaccine and conditional secondary immunogenicity objectives for participants primed with an mRNA vaccine are both achieved, then 1 conditional secondary endpoint on GMT for CoV2 preS dTM-AS03 (B.1.351) or CoV2 preS dTM-AS03 (D614 + B.1.351), will be tested separately.

Conditional secondary objective 2: superiority to the comparator in terms of GMT against B.1.351:

For participants, 18-55 years of age, primed with the Pfizer/BioNTech vaccine, 14 days after the booster dose (ie, D15) of CoV2 preS dTM-AS03 (B.1.351) (non-exploratory arm only) or CoV2 preS dTM-AS03 (D614 + B.1.351), GMT against B.1.351 of CoV2 preS dTM-AS03 (B.1.351) or/and CoV2 preS dTM-AS03 (D614 + B.1.351) is superior to the GMT against B.1.351 of the primary vaccination Comparator Group.

Null hypothesis (H_0) : $\text{GMT}_{(\text{variant})} / \text{GMT}_{(\text{comparator})} \leq 1.5$

Alternative hypothesis (H_1) : $\text{GMT}_{(\text{variant})} / \text{GMT}_{(\text{comparator})} > 1.5$

Each of the 2 variant-containing vaccine groups, CoV2 preS dTM-AS03 (B.1.351) or CoV2 preS dTM-AS03 (D614 + B.1.351), will be tested separately. The superiority will be demonstrated if the lower limit of the two-sided 98.3% CI of the ratio of the GMT is greater than 1.5 for each or both variant-containing vaccine group(s).

If the primary immunogenicity objective in participants primed with the Pfizer/BioNTech vaccine, conditional secondary immunogenicity objective in participants primed with an mRNA vaccine, and conditional secondary immunogenicity objective on GMT in participants primed with the Pfizer/BioNTech vaccine are all achieved. Conditional secondary immunogenicity objective on

seroresponse for participants primed with the Pfizer/BioNTech vaccine and an mRNA vaccine will be tested sequentially.

Conditional secondary objective 3: non-inferiority in terms of seroresponse rate for participants primed with the Pfizer/BioNTech or mRNA vaccines:

For participants, 18-55 years old, primed with the Pfizer/BioNTech vaccine or an mRNA vaccine, 14 days after the booster dose (ie, D15) with CoV2 preS dTM-AS03 (B.1.351) or CoV2 preS dTM-AS03 (D614 + B.1.351) and 14 days after the second dose (ie, D36) of the Comparator Group, the seroresponse rate against D614G (if the SARS-CoV-2 D614G variant remains in circulation globally based on reports from authorities [eg, WHO]) and B.1.351 of the Booster Group CoV2 preS dTM-AS03 (D614), is non-inferior to the seroresponse rate against D614G of the Comparator Group.

Null hypothesis (H0) : $p_{(\text{booster})} - p_{(\text{comparator})} \leq -10\%$

Alternative hypothesis (H1) : $p_{(\text{booster})} - p_{(\text{comparator})} > -10\%$

Each of the 2 Booster Groups, CoV2 preS dTM-AS03 (B.1.351) or CoV2 preS dTM-AS03 (D614 + B.1.351), will be tested separately. The Pfizer/BioNTech vaccine primed and mRNA vaccine primed will be tested sequentially. The non-inferiority will be demonstrated for either or both of the Booster Groups(s) if the lower limit of the two-sided 98.3% CI of the difference between the 2 proportions is great than -10%.

9.2 Sample Size Determination

9.2.1 Original Phase II Cohort of VAT00002

A total of 720 participants are planned to be enrolled. The 3 adjuvanted vaccine groups have a planned sample size of 240 participants in each group. While formal hypothesis testing will not be performed, the targeted sample size is intended to generate sufficient evidence to enable comparison of immune responses generated in this study to those generated by efficacious vaccines (either in the literature or through testing of historical samples from clinical studies with an efficacious vaccine) to inform decisions about progression to and formulation selection for further investigation at Phase III. A sample size of 130 evaluable naïve participants per group enables detecting a minimum observed GMT ratio of 0.73 assuming GMT ratio of 1 and standard deviation of 0.67 (estimated for the Pseudovirus assay) with 95% probability. To generate data in SARS-CoV-2 non-naïve participants, up to 20% of participants may be rapid serodiagnostic test positive at baseline.

An attrition rate of roughly 15% is assumed in the study to account for the potential deployment and availability of authorized/approved vaccines to study participants.

9.2.2 Supplemental Phase III Cohorts 1 and 2

A Bonferroni adjustment is used to control the overall type I error rate at 0.025 one-sided in Supplemental Cohorts 1 and 2, so each comparison of the Booster Group with the Comparator Group will be performed at one-sided significance level of 0.00833 (0.025/3). No alpha-splitting within hypothesis testing of co-primary endpoints. Assumed attrition rate of Primary Vaccination Group is 10% and Booster Group is 3% (it is anticipated that attrition to 14 days post booster will

be limited and smaller than the attrition to D36 in the Comparator Group). Other assumptions for sample size calculation are as follows:

- The PsVN Std Dev is around 0.65 for primary vaccination at D36 and around 1.0 for booster vaccination at D22 on \log_{10} scale base on immunogenicity data obtained from Monogram for the corresponding assay
 - Note : The assumption of the standard deviation of the assay is based on the final interim data of D614G on the PPAS Naïve-D01+D22 at D36 and FAS NonNaïveD01 at D22 from VAT0002 Original Phase II Cohort in participants 18-55 years of age.
- For the primary and secondary objectives in terms of GMT non-inferiority against the comparator (using the D614G titers elicited by the comparator as the benchmark), the ratio of group GMT margin is 1/1.5, the assumed true ratio of group GMT for D614 containing vaccines (comparing D614G titers in both booster vaccine and priming comparator) is 1.5 (this is informed by preliminary interim data from VAT0002 Original Phase II Cohort, indicating titers generally higher in the non-naïve individuals after a single dose, compared to the titers in naïve individuals after 2 doses); and the assumed true ratio of group GMT for the B1.351 variant-containing vaccines (comparing B.1.351 titers in variant-containing vaccines versus D614G titers in the comparator D614 vaccine) is 1 (this is assumed in the absence of data).
- For the primary and secondary objectives in terms of superiority on ratio of serum neutralization titer (post-booster compared to pre-booster), the margin of ratio is 2, and the assumed true ratio is 5 (this is a conservative assumption informed by interim data from VAT0002 Original Phase II Cohort for non-naïve individuals indicating ratio of individual serum neutralization titer for D614G post single immunizations compared to baseline in the range of 14-16). Std Dev 1.0 difference on \log_{10} scale is assumed for the post/pre antibody response.
- For the conditional secondary objective in Supplemental Cohort 2 on superiority of B.1.351 strain (Booster Group versus Comparator Group), the margin of ratio is 1.5, and the assumed true ratio is 3 (this is assumed in the absence of data).
- For the conditional secondary objective on seroresponse (Booster Group at D15 versus Comparator Group at D36), the margin of proportion difference is -10%, the assumed true seroresponse rate for the Booster Group is around 96.5% (this is assumed in the absence of data) and for the Comparator Group is 99%.

For non-inferiority testing of the difference between 2 means (ratio of group GMT on \log_{10} scale), the sample size estimation used a one-sided, two-sample t-test. For superiority by a margin tests for paired means, a one-sided t-test was used.

For the vaccine groups undergoing hypothesis testing, a total of 215 participants, 18-55 years of age, are planned to be enrolled in Supplemental Cohort 1 CoV2 preS dTM-AS03 (D614) vaccine groups.

A total of 515 participants, 18-55 years old, primed with the Pfizer/BioNTech vaccine are planned to be enrolled in each of the 2 Supplemental Cohort 2 vaccine groups, CoV2 preS dTM-AS03 (B.1.351) or CoV2 preS dTM-AS03 (D614 + B.1.351).

A total of 75 participants 18-55 years of age and 25 participants \geq 56 years of age who have received each of the priming vaccines other than those primed with Pfizer/BioNTech, Moderna, Oxford University/AstraZeneca, and J&J/Janssen, are planned to be enrolled to receive the CoV2 preS dTM-AS03 (D614) booster in Supplemental Cohort 1, and the monovalent (B.1.351) booster and CoV2 preS dTM-AS03 (D614 + B.1.351) booster in Cohort 2.

A total of 515 participants, 18-55 years of age, who are SARS-CoV-2 naïve (no evidence of previous infection or vaccination) receiving 2 doses of the CoV2 preS dTM-AS03 (D614) parental vaccine will be enrolled as the Comparator Group for both Supplemental Cohorts 1 and 2.

Additionally, for enabling extrapolation, approximately 50 participants \geq 56 years of age are planned to be enrolled in each Supplemental Cohort 1 and Cohort 2 groups primed with the Pfizer/BioNTech vaccine (in the non-exploratory arms).

Approximately 300 participants, 18-55 years of age, primed with the CoV2 PreS dTM-AS03 vaccine and 150 participants, \geq 56 years of age, primed with the CoV2 PreS dTM-AS03 vaccine are assumed to transition from the Original Phase II Cohort into the 2 Supplemental Cohort 2 vaccine groups, CoV2 preS dTM-AS03 (B.1.351) and CoV2 preS dTM-AS03 (D614); however, the actual number of Original Phase II Cohort participants meeting eligibility criteria for transition cannot be accurately determined, and as such the actual number of CoV2 PreS dTM-AS03 booster participants in Supplemental Cohort 2 may be smaller or larger than assumed. For detailed power estimations for Supplemental Cohorts 1 and 2 refer to [Table 9.1](#).

Table 9.1: Power estimations for Supplemental Cohorts 1 and 2 (18-55 years old)

Cohort/ Objective(s)	Arm	Parameters for Non- inferiority	Parameters for Superiority	Study Power
Cohort 1 CoV2 preS dTM-AS03 (D614) Booster Group				
Primary Objectives (Type I error: 0.00833)	Pfizer primed CoV2 preS dTM-AS03 (D614) Booster Group (N=215)	
 Assumed true ratio of group GMT: 1.5 Margin: 1/1.5 Std Dev (booster): 1.0 Std Dev (comparator): 0.65 	
 Assumed true ratio: 5 Margin: 2 Std Dev (booster): 1.0 	
 Non-inferiority: 98.7% Superiority: > 99.9% Overall: 98.7%
Conditional Secondary Objectives (Type I error: 0.00833)	Protein-based primed CoV2 preS dTM-AS03 (D614) Booster Group (N~=270)			
 Non-inferiority: 99.7% Superiority: > 99.9% Overall: 99.6%
Conditional Secondary Objectives (Type I error: 0.00833)	mRNA primed CoV2 preS dTM- AS03 (D614) Booster Group (N=290)			
 Non-inferiority: 99.8% Superiority: > 99.9% Overall: 99.8%
Conditional Secondary Objectives (Type I error: 0.00833)	Adenovirus vector primed CoV2 preS dTM-AS03 (D614) Booster Group (N=150)			
 Non-inferiority: 94% Superiority: 99.1% Overall: 93.2%
Conditional Secondary Objective	Pfizer primed CoV2 preS dTM-AS03	Non-inferiority on seroresponse		95.3%

(Type I error: 0.00833)	(D614) Booster Group (N=215)	
 Assumed true Comparator Group seroresponse rate: 99% Assumed actual difference between Booster and Comparator Groups: -2.5% Margin: -10% 		
Conditional Secondary Objectives (Type I error: 0.00833)	Protein-based primed CoV2 preS dTM-AS03 (D614) Booster Group (N=270)		98.9%	
Conditional Secondary Objective (Type I error: 0.00833)	mRNA primed CoV2 preS dTM-AS03 (D614) Booster Group (N=290)		99.4%	
Conditional Secondary Objective (Type I error: 0.00833)	Adenovirus vector primed CoV2 preS dTM-AS03 (D614) Booster Group (N=150)		78.2%	
Cohort 2 CoV2 preS dTM-AS03 (B.1.351) Booster Group				
Primary Objectives (Type I error: 0.00833)	Pfizer primed CoV2 preS dTM-AS03 (B.1.351) Booster Group (N=515)	
 Assumed true ratio of group GMT: 1 Margin: 1/1.5 Std Dev (booster): 1.0 Std Dev (comparator): 0.65 	
 Assumed true ratio: 5 Margin: 2 Std Dev (booster): 1.0 
 Non-inferiority: 80.5% Superiority: > 99.9% Overall: 80.5% 	
Conditional Secondary Objectives (Type I error: 0.00833)	mRNA primed CoV2 preS dTM-AS03 (B.1.351) Booster Group (N=590)		
 Non-inferiority: 84.5% Superiority: > 99.9% Overall: 84.5% 	
Conditional Secondary Objective on B.1.351 variant (Type I error: 0.00833)	Pfizer primed CoV2 preS dTM-AS03 (B.1.351) booster group (N=515)	
Superiority on ratio of group GMT (GMT against B.1.351 vs comparator GMT against B.1.351)
 
 Assumed true ratio of group GMT: 3 Margin: 1.5 Std Dev (booster): 1.0 Std Dev (comparator): 0.65 	> 99.9%	
Conditional Secondary Objective on seroresponse (Type I error: 0.00833)	Pfizer primed CoV2 preS dTM-AS03 (B.1.351) booster group (N=515)	
Non-inferiority on seroresponse
 
 Assume true comparator group seroresponse rate: 99% Assumed actual difference between booster and comparator group: -2.5% Margin: -10% 	> 99.9%	
Conditional Secondary Objective on seroresponse (Type I error: 0.00833)	mRNA primed CoV2 preS dTM-AS03 (B.1.351) booster group (N=590)		> 99.9%	
Cohort 2 CoV2 preS dTM-AS03 (D614 + B.1.351) Booster Group				
Primary Objectives (Type I error: 0.00833)	Pfizer primed CoV2 preS dTM-AS03 (D614 + B.1.351) Booster Group (N=515)	
B.1.351 variant:
 
 Assumed true ratio of group GMT: 1 Margin: 1/1.5 Std Dev (booster): 1.0 	
 Assumed true ratio: 5 Margin: 2 Std Dev (booster): 1.0 	
 Non-inferiority (B.1.351 variant): 80.5% Non-inferiority (D614G variant): > 99.9%

		
 Std Dev (comparator): 0.65 
D614 variant:
 
 Assumed true ratio of group GMT: 1.5 Margin: 1/1.5 Std Dev (booster): 1.0 Std Dev (comparator): 0.65 		
 Superiority: > 99.9% Overall (across two strains): 80.5%
Conditional Secondary Objectives (Type I error: 0.00833)	mRNA primed CoV2 preS dTM-AS03 (D614 + B.1.351) Booster Group (N=590)			
 Non-inferiority (B.1.351 variant): 84.5% Non-inferiority (D614 variant): > 99.9% Superiority: > 99.9% Overall (across two strains): 84.5%
Conditional Secondary Objective on B.1.351 variant (Type I error: 0.00833)	Pfizer primed CoV2 preS dTM-AS03 (D614 + B.1.351) Booster Group (N=515)	
Superiority on ratio of group GMT (GMT against B.1.351 vs comparator GMT against B.1.351)
 
 Assumed true ratio of group GMT: 3 Margin: 1.5 Std Dev (booster): 1.0 Std Dev (comparator): 0.65 		> 99.9%
Conditional Secondary Objective on seroresponse (Type I error: 0.00833)	Pfizer primed CoV2 preS dTM-AS03 (D614 + B.1.351) Booster Group (N=515)	
Non-inferiority on seroresponse
 
 Assumed true Comparator Group seroresponse rate: 99% Assumed actual difference between Booster and Comparator groups: -2.5% Margin: -10% 		> 99.9%
Conditional Secondary Objective on seroresponse (Type I error: 0.00833)	mRNA primed CoV2 preS dTM-AS03 (D614 + B.1.351) Booster Group (N=590)			> 99.9%

Note: Std Dev of 0.65 for the comparator at D36, 1.0 for the boosters at D22 were on log₁₀ scale and 1.0 for the post/pre booster at D15 relative to D01 was on log₁₀ scale.

A total of 75 participants 18-55 years of age and 25 participants \geq 56 years of age who have been primed with the Pfizer/BioNTech vaccine are planned to be enrolled to receive the different monovalent (B.1.351) booster formulations in Supplemental Cohort 2. The sample sizes are not based on hypothesis to be tested but rather to provide information on potential future adjustments of the booster vaccines.

9.3 Analysis Sets

The following subgroup definitions of SARS-CoV-2 Naïve and Non-Naïve at D01 or both D01 and D22 timepoints are applied for all randomized participants in the Original Phase II Cohort:

Prior SARS-CoV-2 infection status (Original Phase II Cohort)	Description
SARS-CoV-2 Naïve at baseline (Naïve-D01)	
• Negative by the anti-S immunoassay (Roche Elecsys) on D01 serum sample AND 
• Negative by the anti-N immunoassay on D01 serum sample AND 
• Negative NAAT for SARS-CoV-2 on respiratory sample collected on D01
SARS-CoV-2 Non-Naïve at baseline (Non-Naïve-D01)	
• Positive by the anti-S immunoassay (Roche Elecsys) on D01 serum sample OR 
• Positive by the anti-N immunoassay on D01 serum sample OR 
• Positive NAAT for SARS-CoV-2 on respiratory sample collected on D01
SARS-CoV-2 Naïve at second injection (Naïve-D01+D22)	
• Negative by the anti-S immunoassay (Roche Elecsys) on D01 serum sample AND 
• Negative by anti-N immunoassay on D01 and D22 serum sample AND 
• Negative NAAT for SARS-CoV-2 on respiratory sample collected on D01 and D22
SARS-CoV-2 Non-Naïve at second injection (Non-Naïve-D01/D22)	
• Positive by the anti-S immunoassay (Roche Elecsys) on D01 serum sample OR 
• Positive by the anti-N immunoassay on D01 or D22 serum sample OR 
• Positive NAAT for SARS-CoV-2 on respiratory sample collected on D01 or D22

The following subgroup definitions of SARS-CoV-2 Naïve and Non-Naïve at D01 timepoint are applied for all randomized participants in all Supplemental Cohorts:

Prior SARS-CoV-2 infection status (Supplemental Cohorts)	Description
SARS-CoV-2 Naïve at baseline (Naïve-D01)	
• Negative by the anti-S immunoassay (Roche Elecsys) on D01 serum sample 
AND
 
• Negative NAAT for SARS-CoV-2 on respiratory sample collected on D01
SARS-CoV-2 Non-Naïve at baseline (Non-Naïve-D01)	
• Positive by the anti-S immunoassay (Roche Elecsys) on D01 serum sample 
OR
 
• Positive NAAT for SARS-CoV-2 on respiratory sample collected on D01

The following subgroup definitions of SARS-CoV-2 Naïve and Non-Naïve at both D01 and D22 timepoints are applied for all randomized participants in the Supplemental Cohorts Comparator Group:

Prior SARS-CoV-2 infection status (Supplemental Cohorts)	Description
SARS-CoV-2 Naïve at second injection (Naïve-D01+D22)	
• Negative by the anti-S immunoassay (Roche Elecsys) on D01 serum sample 
AND
 
• Negative NAAT for SARS-CoV-2 on respiratory sample collected on D01 and D22
SARS-CoV-2 Non-Naïve at second injection (Non-Naïve-D01/D22)	
• Positive by the anti-S immunoassay (Roche Elecsys) on D01 serum sample 
OR
 
• Positive NAAT for SARS-CoV-2 on respiratory sample collected on D01 or D22

The following populations are defined for analysis:

Population	Description
Screened	All participants screened for potential study enrollment will be included regardless of being enrolled or not being enrolled. The screening includes the SARS-CoV-2 rapid serodiagnosis test results, demographic information (age, ethnic/racial population, high-risk medical conditions), inclusion/exclusion criteria and prior vaccination platform for booster vaccination groups. The participants reaching the enrollment cap identified in IRT will be excluded from the study enrollment and will have no participant ID assigned.
Randomized	All participants with a randomized group that have been allocated by IRT.
Safety Analysis Set (SafAS)	Participants randomized and who have received at least 1 dose of the study vaccines. All participants will have their safety data analyzed after each dose according to the vaccine they truly received, and after any dose according to the vaccine received at the first dose. Safety data recorded for participants not administered a study intervention will be excluded from the analysis (and listed separately).
Full analysis set (FAS)	All randomized participants who receive at least 1 study injection. Participants will be analyzed according to the intervention to which they were randomized.
Per-protocol analysis set (PPAS)	Subset of the FAS. Participants presenting with at least 1 of the following criteria will be excluded from the PPAS: 
• Participant did not meet all protocol-specified inclusion criteria or met at least one of the protocol-specified exclusion criteria• Participants did not receive both injections for 2 doses primary vaccination groups or 1 dose booster injection for booster vaccination groups• Participant received a vaccine other than the one that he / she was randomized to receive• Preparation and / or administration of vaccine was not done as per-protocol• Participant did not receive protocol defined vaccine in the proper time window• Participants who did not provide all post-dose blood samples within the proper time window or no post-dose blood sample was drawn• Participant received the second injection (in the primary vaccination groups) despite meeting any of the definitive contraindication criteria• Participant receives an authorized/approved COVID-19 vaccine prior to D36 for primary vaccination groups or D15 for booster vaccination groups The definition may be complemented with additional criteria for exclusion after the review of protocol deviations reported on site.

Cellular Immunity and Mucosal analysis set (CMIAS)	
Subset of the FAS and randomly assigned to the Cellular Immunity and mucosal subset (Original Phase II Cohort, Supplemental Cohort 2 primed with the Pfizer/BioNTech vaccine in the non-exploratory groups and Supplemental Cohort 2 CoV2 preS dTM-AS03 (D614) primary series from the Original Phase II Cohort). Participants presenting with at least one of the following criteria will be excluded from the CMIAS:
 
• Participant did not meet all protocol-specified inclusion criteria or met at least one of the protocol-specified exclusion criteria• Participants did not receive both injections in the primary vaccination groups or one injection in the booster vaccination groups• Participant received a vaccine other than the one that he / she was randomized to receive• Preparation and / or administration of vaccine was not done as per-protocol• Participant did not receive vaccine in the proper time window• Participants received the second injection (in the primary vaccination groups) despite meeting any of the definitive contraindication criteria.• Participant receives an authorized/approved COVID-19 vaccine prior to D36 for primary vaccination groups or D15 for booster vaccination groups 
The definition may be complemented with additional criteria for exclusion after the review of protocol deviations reported on site.

Variant Testing analysis set (VTAS)	
Subset of the FAS and randomly assigned to the Variant Testing subset: Supplemental Cohort 1, Supplemental Cohorts 1 and 2 Comparator Group, Supplemental Cohort 2 primed with the Pfizer/BioNTech vaccine in the non-exploratory groups and Supplemental Cohort 2 CoV2 preS dTM-AS03 (D614) primary series from the Original Phase II Cohort. Participants presenting with at least 1 of the following criteria will be excluded from the VTAS:
 
• Participant did not meet all protocol-specified inclusion criteria or met at least one of the protocol-specified exclusion criteria• Participants did not receive both injections in the primary vaccination groups or one injection in the booster vaccination groups• Participant received a vaccine other than the one that he / she was randomized to receive• Preparation and / or administration of vaccine was not done as per-protocol• Participant did not receive vaccine in the proper time window• Participants received the second injection (in the primary vaccination groups) despite meeting any of the definitive contraindication criteria.• Participant receives an authorized/approved COVID-19 vaccine prior to D36 for primary vaccination groups or D15 for booster vaccination groups

	The definition may be complemented with additional criteria for exclusion after the review of protocol deviations reported on site.
--	---

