8.1.5.3 ELECSYS Anti-SARS-CoV-2 Anti-N ECLIA

This test was to be used on D01 and D22 samples to determine naïve and non-naïve status in participants in the Original Phase II Cohort. Details were provided in the Operating Guidelines and the PPD laboratory manual. Based on data from the Original Phase II Cohort, the performance of this test is very similar to that of the ELECSYS Anti-SARS-CoV-2 Anti-S ECLIA described below, but the sensitivity of the ELECSYS Anti-SARS-CoV-2 Anti-S ECLIA is marginally higher. Therefore, it is considered that the ELECSYS Anti-SARS-CoV-2 Anti-N ECLIA is not adding meaningful value beyond the ELECSYS Anti-SARS-CoV-2 Anti-S ECLIA for determination of naïve vs. non-naïve status in the priming groups included in the Supplemental Cohorts.

ELECSYS Anti-SARS-CoV-2 is an immunoassay intended for qualitative detection of antibodies to SARS-CoV-2 in human serum. The ELECSYS Anti-SARS-CoV-2 assay uses a recombinant protein representing the nucleocapsid (N) antigen for the determination of antibodies against SARS-CoV-2. Sample, biotinylated SARS-CoV-2 specific recombinant antigen and SARS-CoV-2 specific recombinant antigen labeled with a ruthenium complex are first incubated and form a sandwich complex. After addition of streptavidin-coated microparticles, the complex becomes bound to the solid phase via interaction of biotin and streptavidin. The reaction mixture is aspirated into the measuring cell where the microparticles are magnetically captured onto the surface of the electrode. Unbound substances are then removed with ProCell/ProCell M/ProCell II M. Application of a voltage to the electrode then induces chemiluminescent emission which is measured by a photomultiplier. Results are determined automatically by the software by comparing the electrochemiluminescence signal obtained from the reaction product of the sample with the signal of the cutoff value previously obtained by calibration.

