8.1.5.4 ELECSYS Anti-SARS-CoV2 Anti-S ECLIA

This test will be used on D01 samples in all participants belonging to any groups evaluating priming vaccines (Original Phase II Cohort and the Supplemental Cohorts Comparator Group) to determine naïve and non-naïve status. Details will be provided in the Operating Guidelines and the PPD laboratory manual. This testing will be performed in all Cohorts.

ELECSYS Anti-SARS-CoV-2 is an immunoassay intended for qualitative detection of antibodies to SARS-CoV-2 in human serum. The ELECSYS Anti-SARS-CoV-2 assay uses a recombinant protein representing the S antigen for the determination of antibodies against SARS-CoV-2. Sample, biotinylated SARS-CoV-2 specific recombinant antigen and SARS-CoV-2 specific recombinant antigen labeled with a ruthenium complex are first incubated and form a sandwich complex. After addition of streptavidin-coated microparticles, the complex becomes bound to the solid phase via interaction of biotin and streptavidin. The reaction mixture is aspirated into the measuring cell where the microparticles are magnetically captured onto the surface of the electrode. Unbound substances are then removed with ProCell/ProCell M/ProCell II M.

Application of a voltage to the electrode then induces chemiluminescent emission which is measured by a photomultiplier. Results are determined automatically by the software by comparing the electrochemiluminescence signal obtained from the reaction product of the sample with the signal of the cutoff value previously obtained by calibration.

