8.3.4 ELECSYS Anti-SARS-CoV-2 Anti-N ECLIA

SARS-CoV-2 anti-nucleocapsid antibodies will be measured using the Roche ELECSYS Anti-SARS-CoV-2 ECLIA on all blood samples in participants for ascertainment of serologically-confirmed SARS-CoV-2 infection in participants belonging to the Original Phase II Cohort. In addition, this test will be used on D01 and D22 samples for the Original Phase II Cohort in all participants to aid in determination of naïve and non-naïve status (see [Section 8.1.5.3](#)). Details will be provided in the Operating Guidelines and the PPD laboratory manual.

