9.1.2.1 A Pooled Primary Series Cohort as Supplemental Cohort 2 Comparator Group

As the number of authorized and/or approved COVID-19 vaccines increases, promptly enrolling the planned 515 naïve participants into the Comparator Group shared by Supplemental Cohorts 1 and 2 may become unattainable. In order to maintain sufficient target power for Supplemental Cohort 2 hypothesis testing, in case of a substantial shortfall in numbers of naïve Comparator Group participants, a pooled primary series cohort with a sample size of at least 464 (a 10% dropout rate from 515) evaluable participants may be planned to serve as the Comparator Group for Supplemental Cohort 2.

Participants in this pooled primary series cohort will be added from 2 potential sources, in the following order:

1. All SARS-CoV-2-naïve participants contemporaneously enrolled in Supplemental Cohort 1
2. Eligible participants from studies involving the same CoV2 preS dTM-AS03 vaccine
 - a) Eligible participants in the VAT00002 Original Phase II Cohort
 - b) Eligible participants in other studies of this same investigational SARS-CoV-2 vaccine program

Evaluable participants will be pooled in sequence from the above sources. Eligible participants will be selected and pooled base on the comparability of population and assessments per clinical justification outlined in the SAP.

An exploratory sensitivity analysis will be performed on the hypothesis testing for Supplemental Cohort 2 to test the robustness of the primary analyses by using the pooling primary series as the Comparator Group.

9.1.2.2 Supplemental Cohort 1

Hypothesis testing will be conducted for the 2 co-primary immunogenicity endpoints in participants, 18-55 years old, primed with the Pfizer/BioNTech vaccine, 2 conditional co-secondary immunogenicity endpoints in participants, 18-55 years old, primed with the protein-based vaccine, 2 conditional co-secondary immunogenicity endpoints in participants, 18-55 years old, primed with an mRNA vaccine, 2 conditional co-secondary immunogenicity endpoints in participants, 18-55 years old, primed with an adenovirus vector vaccine, 1 conditional secondary immunogenicity endpoint on seroresponse in participants, 18-55 years old, primed with the Pfizer/BioNTech vaccine, the protein-based vaccine, an mRNA vaccine, and an adenovirus vector vaccine sequentially.

Primary objective 1: non-inferiority to the comparator for participants primed with the Pfizer/BioNTech vaccine:

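### The Comparator Group's Naïve-D01+D22 definition drops the D22 anti-N test for a reason that holds only before vaccination

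*Protocol*

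**What the plan says.** Section 9.3 defines Naïve-D01+D22 twice. For the Original Phase II Cohort it requires "Negative by anti-N immunoassay on D01 and D22 serum sample", together with negative anti-S on D01 and negative NAAT on D01 and D22. For the Comparator Group it requires "Negative by the anti-S immunoassay (Roche Elecsys) on D01 serum sample" and "Negative NAAT for SARS-CoV-2 on respiratory sample collected on D01 and D22", with no anti-N at either visit. Table 8.3 has no anti-N row for this group and does not list the multiplex ECLIA that contains the N antigen. Section 8.3.4 places follow-up anti-N testing in the Phase II cohort, "for ascertainment of serologically-confirmed SARS-CoV-2 infection in participants belonging to the Original Phase II Cohort".

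Section 8.1.5.3 gives the reason: on Phase II data, "the ELECSYS Anti-SARS-CoV-2 Anti-N ECLIA is not adding meaningful value beyond the ELECSYS Anti-SARS-CoV-2 Anti-S ECLIA for determination of naïve vs. non-naïve status" in the Supplemental priming groups. Section 8.1.5.4 fixes when the remaining serological test is run: "This test will be used on D01 samples in all participants belonging to any groups evaluating priming vaccines".

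Table 9.2 names PPAS Naïve at D01+D22 as the per-protocol comparator set for both Supplemental Cohorts, with two FAS versions alongside. If comparator enrolment falls well short, section 9.1.2.1 allows a pooled comparator for Cohort 2 whose sources include "Eligible participants in the VAT00002 Original Phase II Cohort".

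**The concern.** The rationale compares anti-N with anti-S as markers of past infection. Before vaccination the two compete, and dropping the slightly less sensitive one is reasonable. At D22 they do not compete. The participant has received a Spike antigen, anti-S is not run, and if it were run it could not separate infection from vaccination. Section 8.1.5.2 itself warns that vaccine-induced seropositivity makes antibody tests hard to interpret, and section 8.3.1 defines serologically confirmed infection by nucleocapsid antibody. Anti-N is therefore the only serological marker of an infection acquired between the two doses, and the stated reason does not reach it.

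At stake is how clean the shared benchmark is. A comparator infected between doses is likely to have a higher D36 titre than the naïve two-dose response named in the objectives, and would pull the comparator GMT up. The planning SD of 0.65 in section 9.2.2 was also taken from the Phase II set of the same name, which was screened for anti-N.

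**Working it through.** **1. The two definitions side by side (section 9.3)**

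| Requirement | Original Phase II Cohort | Comparator Group |
|---|---|---|
| Anti-S, D01 | negative | negative |
| Anti-N, D01 | negative | not tested |
| Anti-N, D22 | negative | not tested |
| NAAT, D01 and D22 | negative | negative |

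**2. What already removes between-dose infections**
- DCI04 (section 7.1.2): NAAT-confirmed infection before V02 bars the second dose.
- PPAS (section 9.3): excludes anyone without both doses, or dosed despite a definitive contraindication.
- A positive D22 NAAT makes the participant non-naïve.
- Symptoms are reported passively throughout and asked about at visits and calls before D43 (section 8.3.2). Two-weekly active contact starts at D43.

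The residue is an infection between D01 and D22 that was never NAAT-tested and is NAAT-negative on D22. D22 anti-N recovers only those who have seroconverted by then.

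**3. Reproducing the plan's power (section 9.2.2, Table 9.1)**

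Inputs: one-sided alpha 0.025/3; log10 SD 1.0 (booster) and 0.65 (comparator); margin 1/1.5; true B.1.351 ratio 1; 515 × 0.97 = 499 boosters and 515 × 0.90 = 463 comparators.

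SE = √(1.0²/499 + 0.65²/463) = 0.054. The difference to detect is log10(1.5) = 0.176. A one-sided t-test with unequal variances (noncentral t) gives 80.5%, as stated. The Cohort 1 Pfizer-primed test (208 boosters, true ratio 1.5) gives 98.7%, also as stated.

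**4. Illustration of missed infections**

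Let a share f of comparators have titres k times higher, with SD 1.0. The comparator mean rises by f·log10(k), and its SD becomes √[(1−f)·0.65² + f·1.0² + f(1−f)·(log10 k)²]. The documents give no value for f; 1% to 2% is assumed. For k, use the 10 µg ratio in Table 4.6: 13039/3961 = 3.29, so log10(k) = 0.517.

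| f | GMT factor | Comparator SD | Cohort 2 power | Cohort 1 power |
|---|---|---|---|---|
| 0 | 1.000 | 0.650 | 80.5% | 98.7% |
| 1% | 1.012 | 0.656 | 77.5% | 98.5% |
| 2% | 1.024 | 0.663 | 74.3% | 98.2% |

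**5. Cost of excluding instead**

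With 1%, 2% or 5% of comparators removed (458, 453 or 439 left), Cohort 2 power is 80.4%, 80.2% or 79.8%.

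**The case against.** Most of the opposing case limits the size of the point, and much of it stands.

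- A reader might infer that between-dose infections generally stay in the benchmark. The documents do not support that: the safeguards in step 2 remove those confirmed by NAAT, and a local NAAT counts. The residue is narrow.
- The illustration is soft. The missed share has no source in the documents. The ratio compares previously infected participants 21 days after one dose with naïve participants at D36, not infection between doses followed by dose 2. It rests on 12 non-naïve participants, with a 95% CI of 3175 to 53540 that overlaps the naïve interval of 2795 to 5612. A 5% share would give much lower power (63.4%), but that means about 23 of 463 comparators infected, unswabbed and cleared within three weeks, and nothing in the protocol supports it.
- A reader might suspect a bias towards the boosters. The direction is the opposite: missed infections raise the bar.
- A reader might infer that pooling will necessarily mix two definitions. Pooling is conditional on a shortfall, and selection on comparability is left to the SAP. The Phase II rule is also strictly tighter, so every Phase II participant who meets it also meets the Comparator rule, and one common (looser) definition is available without new testing.

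None of this answers the central point. The reason given for omitting anti-N does not apply to the D22 sample, and without a Comparator result the SAP could apply the stricter rule only by testing stored serum.

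**Conclusion.** The point holds as a cheap improvement. One label carries two rules, and the justification covers only the pre-vaccination half of the change. The consequence is limited to infections that NAAT did not catch. They would work against the booster candidates, cost power mainly in the Cohort 2 B.1.351 non-inferiority tests, and do not inflate type I error.

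On an assumed missed share of 1% to 2%, and with 3.29 as a proxy for the titre effect, the loss is about 3 to 6 power points from 80.5%. Only the part that has seroconverted by D22 is recoverable. Cohort 1 loses about half a point at most. No stated figure in the protocol is wrong.

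**What to change.** In section 9.3, add a negative anti-N immunoassay on the D22 serum to the Comparator Group's Naïve-D01+D22 definition, and add a positive D22 anti-N to Non-Naïve-D01/D22. Run the assay on the D22 serum already drawn (BL0002) and add the row to Table 8.3.

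For D01, either add anti-N as well, so that the label means the same in both cohorts, or state that D01 anti-N is omitted for the reason in section 8.1.5.3. State one common definition for any Phase II participants pooled under section 9.1.2.1. Keep FAS Naïve at D01 as a supportive set.

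The cost is about 515 extra anti-N assays on existing sera, with a test already in use in this study, some wording, and the loss of a few comparators from the PPAS. That loss is under one power point for exclusions up to 5% (80.5% to 79.8%). Adding D01 anti-N would roughly double the number of assays.
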